2.0 OBJECTIVES

- To determine if the use of steroids decreases the incidence of dysphasia after anterior cervical discectomy and fusion (ACDF).
- If steroids are useful, determine which method of steroid administration is most efficacious (IV versus local application).
- We hypothesize that local application of steroids in ACDF surgery will lead to a decreased incidence of dysphagia, in the postoperative period as compared to intravenous steroids or a control group.
- To evaluate the incidence of dysphonia, as measured by the Voice Handicap Index (VHI-10), as well as other validated outcome measures (NDI, VAS, EQ-5D).

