5.0 STUDY DESIGN & METHODS

We intend to prospectively evaluate 85 patients as part of a single blind, randomized controlled study. Subjects would be randomized to group I (control group, no steroid), group II (10 mg of intraoperative intravenous decadron with gel foam sponge placed on cervical plate), or group III (40mg of triamcinolone on gel foam sponge dabbed on the anterior cervical plate). Subjects will be blinded to the treatment arm. Randomization will take place on the day of surgery. 85 envelopes will be sealed, 25 of which will contain a document specifying “control”, “iv steroids”, or “steroid sponge”. The 75 envelopes will then be shuffled to create a random assortment. The circulating nurse in the OR will at random choose one envelop prior to the start of the operative procedure. This will in turn specify the treatment group for each patient.

There is no standard of care regarding the use of IV or local steroids in the setting of ACDF. Currently, the use of either IV or local steroids is at the discretion of the attending surgeon. To my knowledge, there are several spine surgeons at our institution that currently use no steroid, and others who use a combination of IV and/or local steroids.

The primary outcome measure is the incidence of dysphagia as measured by Eating Assessment Tool (EAT-10) and the Bazaz score. The patients will prospectively fill out these surveys preoperatively, post-operative day 1, week 2, week 6, month 3, month 6, and 1 year as a measure of dysphagia. The standard of care is to see patients in the office at 2 weeks, 6 weeks, 3 months, 6 months, and 1 year after surgery, and therefore, no extra visits will be necessary for this study. X-rays will be taken at 6 weeks, 3

months, and 12 months post-op, which is the current standard of care. No additional x-rays will be obtained.

A secondary outcome measure will be the incidence of dysphonia, as measured by the Voice Handicap Index (VHI-10), as well as other validated outcome measures (NDI, VAS, EQ-5D). The questionnaires will take approximately 20 minutes to complete and will be administered in the hospital, during the post-operative clinic visits with the surgeon, or over the phone. The surgeons will also listen to the patient's voice at these different time points and comment on dysphonia as being absent, mild, moderate, or severe.

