6.0 STATISTICAL PLAN

We will use T score or ANOVA to compare EAT-10 scores, VHI scores, and EQ-5D, and Chi square for subjective findings. The P value will be set at 0.05.

A power analysis was performed to determine the sample size needed. Based on previous studies evaluating the EAT-10 in normal patients and those with dysphasia the analysis concluded: with total sample size 85 (Group I: 25, Group II: 25, Group III: 25) and estimated standard deviation of EAT-10 as 12.7, **power = 0.92**

Drs. [name], [name], and [name], perform approximately 6 ACDFs a month. This would allow us to collect our proposed sample size in approximately 12-14 months.

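### The stated primary is dysphagia incidence on two instruments at six visits, but section 6.0 tests and powers EAT-10 scores, with no deciding visit, instrument or test rule

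*Combined protocol and SAP*

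**What the plan says.** Section 5.0 defines the primary: "The primary outcome measure is the incidence of dysphagia as measured by Eating Assessment Tool (EAT-10) and the Bazaz score". On timing it says: "The patients will prospectively fill out these surveys preoperatively, post-operative day 1, week 2, week 6, month 3, month 6, and 1 year". That is one baseline and six post-operative assessments, and none is named as deciding. It gives no EAT-10 cut-off for a case and no rule for when the instruments disagree.

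Section 2.0 asks first whether steroids help at all, then: "If steroids are useful, determine which method of steroid administration is most efficacious (IV versus local application". It adds a directional hypothesis, "We hypothesize that local application of steroids in ACDF surgery will lead to a decreased incidence of dysphagia, in the postoperative period", set against intravenous steroids or control. The Synopsis repeats that hypothesis.

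On tests, section 6.0 has two sentences: "We will use T score or ANOVA to compare EAT-10 scores, VHI scores, and EQ-5D, and Chi square for subjective findings", and "The P value will be set at 0.05". It does not state sidedness, define the subjective findings, or carry the order of section 2.0 into a test rule. The power of 0.92 is given with "estimated standard deviation of EAT-10 as 12.7". No mean difference and no incidence rates are stated.

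**The concern.** Two linked problems follow.

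- **The power belongs to a different quantity.** An SD of a score cannot power a proportion. That would need a cut-off and event rates, and the plan has neither.
- **The decision rule is open.** Two instruments, six visits and three pairs of arms leave several readings of what would count as success, all at 0.05. If day 1 and week 6 disagree, or EAT-10 and Bazaz disagree, the plan does not say which one answers the question. The choice could then be made after the data are seen, and the false-positive rate would depend on it.

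**Working it through.** **1. The plan's 0.92.** The inputs in section 6.0 are SD 12.7, P at 0.05 and 25 per group. The stated total of 85 does not match 3 × 25 = 75, so 28 per arm (85/3 ≈ 28.3) was also tried. With no difference stated, power cannot be computed forwards, so I solved for the difference Δ.

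- t-test: noncentrality = (Δ/12.7) × √(n/2). Two-sided, power 0.92 needs Δ = 12.3 (n = 25) or 11.6 (n = 28). One-sided, it needs 11.1 or 10.5.
- Three-group ANOVA: effect size f = 0.434 (n = 25) or 0.410 (n = 28). If IV equals control or local, Δ = f × 12.7 × 3/√2 = 11.7 or 11.0. If IV lies halfway, Δ = f × 12.7 × √6 = 13.5 or 12.7.

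So 0.92 corresponds to about 11.0-13.5 points two-sided, or 10.5-11.1 for a one-sided t-test. Below I use 12.4 points, where the two-sided t-test with 25 per arm has power 0.92.

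**2. The same shift as incidence.** Assume normal scores. The shift is 12.4/12.7 = 0.976 SD, and local incidence = Φ(Φ⁻¹(control incidence) − 0.976). Powers use the uncorrected chi-square with 25 per arm.

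| Control | Local | Pairwise power | After a three-group chi-square |
|---|---|---|---|
| 30% | 6.7% | 62% | 45-55% |
| 50% | 16.4% | 75% | 62-70% |
| 70% | 32.6% | 81% | 67-75% |

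That test is also slightly liberal: its pairwise size is 0.054-0.065 for prevalence 0.15-0.7. Fisher's exact test has size 0.019-0.033.

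**3. False benefit under different readings.** Null trials were simulated with 25 per arm and two-sided 0.05 tests (t-test/ANOVA for EAT-10, chi-square for Bazaz). The assumptions, none from the documents, are visit correlation 0.3-0.85, instrument correlation 0.5-0.8 and Bazaz prevalence 15-50%. The count is of trials showing IV or local better than control.

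| Reading | Chance |
|---|---|
| Both instruments agree on the same contrast and visit | 2-8% |
| EAT-10 alone, any visit, after a three-group test at that visit | 5-11% |
| Either instrument, any visit, so gated | 11-21% |
| Either instrument, any visit, ungated | 22-40% |
| As above, also counting local over IV | 32-53% |

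Only one direction is counted. For the first four rows, the benchmark at one visit under a controlled two-sided 5% rule is about 2-2.5%, not 5%.

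**4. A rule that holds 5%.** Take one visit, EAT-10 means, ANOVA at 0.05, and pairwise t-tests at 0.05 only if it is significant. Any false result occurs in 0.050 of trials under the global null, and in 0.049-0.051 when one arm differs by 12.4 or 25 points or both steroid arms differ by 12.4. Local-versus-control power at 12.4 points is 86% if IV is halfway and 91% if IV equals either other arm.

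**5. Choice of time frame.** The SD of a six-visit average is 12.7 × √((1 + 5ρ)/6) = 8.2, 10.4 or 11.9 at visit correlation ρ = 0.3, 0.6 or 0.85. Power under the rule in step 4, with IV halfway, is 91-99% if 12.4 points holds at all visits. If the effect exists only at the first two visits, the average difference is 12.4 × 2/6 = 4.1 points and power is 15-30%. Scoring a case as at or above the cut-off at any of six visits, after a three-group chi-square, does worse in that same situation: about 2-5% at constant prevalence of 30-50%, and 35-42% if prevalence falls over the visits.

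**The case against.** The plan is less open than it first looks. Section 1.0 calls Bazaz subjective and not validated, and section 6.0 gives chi-square to subjective findings and a means test to EAT-10. Read together, Bazaz probably gets the chi-square. Since power is quoted for EAT-10 alone, EAT-10 probably leads. Joining the two instruments with *and* could also mean that both must agree, which is the low-error reading.

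These points stand as inferences. They do not name a visit, fix the contrast or make a score SD apply to incidence. The hint on Bazaz is also weak, because section 1.0 goes on to include Bazaz among measures with excellent validity.

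Three stronger readings are tempting, and the documents do not support them:

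- **That every instrument, visit and pair will be tested at 0.05.** The plan does not say so. The top of the error range describes one permitted reading, not the plan's commitment.
- **That there is no comparison or test order at all.** Section 2.0 has an informal order and a directional hypothesis. The defect is that section 6.0 does not make them a test rule.
- **That 0.92 is a miscalculation.** It is attainable for mean scores at about 12.3 points with 25 per arm. It cannot be checked because the difference is missing.

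**Conclusion.** The point holds, and it needs correcting before data are seen. The mismatch between incidence as the primary and a power statement on scores is wrong as written and depends on no assumption. So is the absence of a deciding visit, instrument and test rule.

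The sizes do depend on assumptions. The fall from 92% to 62-81% power assumes normal scores, a 12.4-point shift, and control incidence of 30-70%. The false-benefit range of about 2% to 40% (53% counting local over IV) rests on assumed correlations and prevalence. It shows how much the unstated rule matters and is not an estimate of this trial's error rate.

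**What to change.** In sections 5.0 and 6.0, before data are seen:

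1. **Choose one primary quantity.** The simplest choice consistent with the power statement is the mean EAT-10 score, with the incidence wording in the Synopsis and sections 2.0 and 5.0 changed to match. If incidence is kept, state the EAT-10 cut-off and how the preoperative score is used, and use exact tests.
2. **Name one primary post-operative visit.** If a six-visit average is preferred, state its cost when the effect is early only. Do not default to a case at any of six visits.
3. **Replace the t-test-or-ANOVA choice for the primary with one two-sided rule that holds 5% and covers the stated hypothesis.** One example is the three-group ANOVA at 0.05, then pairwise tests, including local versus control and local versus IV, only if it is significant. A rule that stops at pooled steroids versus control, then IV versus local, never tests local versus control.
4. **Restate the power** for the quantity, visit and rule chosen, with its target difference and per-arm n.
5. **Report Bazaz and all other visits as secondary**, with estimates and confidence intervals.

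The cost is a few lines of text and no extra data. A Bazaz or other-visit result can no longer be called primary. Under the example rule, local-versus-control power at 12.4 points falls from 92% to about 86-91%. Keeping incidence costs more: exact tests are conservative at 25 per arm, so power would be below the uncorrected chi-square figures above.

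### The stated power of 0.92 is at best a zero-loss figure: as the assignments are specified, 25 per arm are randomised, follow-up runs to 1 year, and no loss allowance is stated.

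*Combined protocol and SAP*

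**What the plan says.** **Section 6.0 (Statistical Plan).** Power of 0.92 is stated "with total sample size 85 (Group I: 25, Group II: 25, Group III: 25) and estimated standard deviation of EAT-10 as 12.7". The source is described only as "Based on previous studies evaluating the EAT-10 in normal patients and those with dysphasia the analysis concluded"; no EAT-10 difference follows. The test is left open ("We will use T score or ANOVA to compare EAT-10 scores, VHI scores, and EQ-5D"), and the level is given as "The P value will be set at 0.05", without saying whether it is one- or two-sided.

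**Section 5.0 (Study Design & Methods).** The plan is to evaluate 85 patients. It seals 85 envelopes and gives 25 to each of the three labels, which makes 75. It then says "The 75 envelopes will then be shuffled to create a random assortment". Ten sealed envelopes have no label and no stated purpose. EAT-10 and the Bazaz score are completed before surgery and at "post-operative day 1, week 2, week 6, month 3, month 6, and 1 year as a measure of dysphagia". No primary time point is named. Subjects may skip questions.

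**Synopsis and appendices.** The synopsis repeats 85 subjects with 25 per group. The coded identifier form and the data collection form each have 75 rows.

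**Not stated anywhere.** There is no expected loss rate, inflation step, replacement rule or missing-data method, and nothing says what the ten patients above 75 are for.

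**The concern.** Every per-arm number in the plan is 25: in the power statement, in the envelope labels and in the synopsis. If 25 per arm are randomised and 0.92 was computed for 25 per arm, the calculation has no margin. Any patient without an EAT-10 score at the analysed visit takes the trial below the stated power. If 0.92 was computed for 85, the specified assignments fall short of it before anyone is lost.

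At stake is how far the stated power can be relied on. A reader takes 0.92 as what the trial will deliver, when it is a ceiling tied to an unclear N. This is a matter of precision only; bias from who drops out is a separate question.

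**Working it through.** **Inputs from Section 6.0:** SD 12.7, level 0.05, power 0.92, and N given as both 85 and 3 × 25 = 75.

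**Assumptions of mine:** a two-sided test, a pairwise t-test as the main case (with ANOVA as a check), equal loss across arms, and loss of 12% to 20%. The documents give no loss rate.

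**Step 1. Reproduce 0.92.** This cannot be done forwards because the EAT-10 difference is missing. I solved for the difference d that gives 0.92 under each reading of N. For n per arm,

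power = P(|T| > t₀.₉₇₅, 2n−2), where T is non-central t with 2n − 2 degrees of freedom and non-centrality (d / 12.7) × √(n / 2).

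- Reading A, n = 25: d = 12.34 (0.971 SD). Non-centrality is 0.971 × √12.5 = 3.43 and the critical value is 2.011, giving power 0.920.
- Reading B, n = 85 / 3 = 28.33: d = 11.56 (0.910 SD). Non-centrality is 0.910 × √14.17 = 3.43 and the critical value is 2.004, giving power 0.920.

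Both readings return 0.92 with a similar difference, so the text cannot show which N was used.

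**Step 2. Hold d fixed and reduce the number analysed from 25 per arm.**

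| Analysed per arm | Loss from 25 | Reading A (d = 12.34) | Reading B (d = 11.56) |
|---|---|---|---|
| 25 | 0% | 0.920 | 0.884 |
| 24 | 4% | 0.909 | 0.870 |
| 23 | 8% | 0.896 | 0.855 |
| 22 | 12% | 0.882 | 0.839 |
| 21 | 16% | 0.867 | 0.821 |
| 20 | 20% | 0.849 | 0.801 |

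**Step 3. Check that the choice of test does not drive the result.** I used a three-group ANOVA with one arm differing, calibrated to 0.92 in the same way. Under reading A (d = 11.70) it gives 0.880, 0.863 and 0.844 at 22, 21 and 20 per arm. Under reading B (d = 10.97) it gives 0.881 at 25 per arm, then 0.832, 0.812 and 0.791 at 22, 21 and 20. Equally spaced means give the same powers once calibrated. All are within about 0.01 of the t-test.

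**Step 4. Suppose 85 are actually randomised.**

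- If 0.92 refers to 75 analysed, power with no loss is 0.949 (28.33 per arm, d = 12.34). The number analysed falls to 75 after (85 − 75) / 85 = 11.8% loss, and power is below 0.92 beyond that. At 20% loss, 85 × 0.8 / 3 = 22.7 per arm remain. That lies between 22.5 (0.890) and 23 (0.896), so power is about 0.89.
- If 0.92 refers to 85 analysed, there is no margin, and 11.8% loss leaves 25 per arm and power 0.884.

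**The case against.** The strongest reply is that the plan says 85 in several places: the synopsis, the planned enrolment, the sealed envelopes and the power sentence itself. The gap of 10 between 75 and 85 is the size of a loss allowance of about 12%, and the absence of a label does not prove that it is not one. On that reading the trial would start near 0.95, and early losses would not take it below 0.92.

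This stands in part. A reader might infer that power drops below 0.92 as soon as any patient is lost. The documents do not support that flatly, because they never settle whether 75 or 85 are randomised, or which of the two 0.92 belongs to. Equally, nothing in them calls the ten patients an allowance. Section 6.0 puts 85 inside the power statement as the total, and Section 5.0 gives ten envelopes no arm. The rescue needs two things the plan does not say: that 85 are assigned, and that 0.92 was computed for 75.

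Two further replies also stand:

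- **Loss may be small at an early visit.** EAT-10 is collected on day 1, the clinic visits are standard care, and questionnaires can be completed by phone. With no primary time point named, the relevant loss rate is unknown.
- **The after-loss figures are conditional.** They combine a back-solved difference with an assumed loss rate, so they should not go into the protocol as established power.

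**Conclusion.** The point holds in conditional form. Under the assignments as specified (25 per arm), 0.92 is at best the power with no loss. With 12% to 20% loss at the analysed visit it is about 0.88 to 0.85 if 0.92 refers to 25 per arm. If 0.92 refers to 85, it is about 0.88 before any loss and about 0.84 to 0.80 after it. It survives only if 85 are randomised and 0.92 refers to 75 analysed, up to about 12% loss.

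The effect is modest: about 0.80 or above in all of these t-test cases, with ANOVA at worst 0.79. It does not show the trial to be underpowered, and a reader should not infer that more patients are required. The results rest on SD 12.7, a two-sided 0.05 level without multiplicity adjustment, equal loss across arms, and a difference solved from 0.92 itself. They concern mean EAT-10 scores. The primary outcome is worded as incidence of dysphagia, so neither 0.92 nor the after-loss figures describe power for an incidence comparison.

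**What to change.** In Section 6.0:

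1. State the EAT-10 difference, the test, the sidedness and the N that 0.92 refers to.
2. Reconcile 85 with 3 × 25, and make the envelope count in Section 5.0 and the synopsis agree with it.
3. Say whether the ten patients above 75 are a loss allowance. If they are, specify which arms their envelopes belong to.
4. Name the visit at which EAT-10 is analysed. State power as conditional on the number analysed at that visit, with the after-loss figure beside the zero-loss one and the loss rate labelled as an assumption.

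The replacement text should not tie 0.92 to 25 per arm until items 1 and 2 are settled; under the other reading that would overstate power by about 0.04 (0.920 − 0.884).

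The cost is a few sentences in Sections 5.0 and 6.0 and the synopsis, and a slightly less favourable stated power. Enrolment does not need to increase.

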A SINGLE BLIND, PROSPECTIVE, RANDOMIZED CONTROLLED TRIAL ON THE EFFECT OF LOCAL STEROID APPLICATION VERSUS INTRAVENOUS STEROIDS ON DYSPHAGIA FOLLOWING ANTERIOR CERVICAL DISECTION AND FUSION

PRINCIPAL INVESTIGATOR: [name], FACS
[name]
[name]
[contact]
[contact]
[contact]

SUB-INVESTIGATORS: [name]
Northwestern University

[name]
Northwestern University

[name], MD
University of Wisconsin-Madison

[name], MD
OrthoCarolina Research Institute

PARTICIPATING SITES: Northwestern Memorial Faculty Foundation
(NMFF)
[name]
[name]
[contact]

Northwestern University (NU)
[name]
[name]

OrthoCarolina Research Institute
[name]
[name]

University of Wisconsin-Madison

FUNDING AGENCY: Cervical Spine Research Society (CSRS)

Synopsis

Title	A single blind, prospective, randomized controlled trial on the effect of local steroid application versus intravenous steroids on dysphagia following anterior cervical discectomy and fusion (ACDF)
Short Title	Effect of local application vs. IV steroids on dysphagia after ACDF
Protocol Date	12/14/2015
Study Duration	2 years
Study Center(s)	Northwestern Memorial Faculty Foundation (NMFF), Northwestern University (NU), University of Wisconsin-Madison, OrthoCarolina Research Institute
Objectives	Local application of steroids in ACDF surgery will lead to decreased incidence of dysphagia compared to intravenous steroids or a control group
Number of Subjects	85 (randomized to group I (control group), group II (10 mg of intraoperative intravenous decadron), or group III (40mg of triamcinolone placed on cervical plate), i.e. 25 per group.
Diagnosis and Main Inclusion Criteria	Patients undergoing ACDF (single or multi-level) for the treatment of radiculopathy or myelopathy by Drs. [name], [name], and [name].

TABLE OF CONTENTS

Synopsis	2
1.0 Introduction	4
2.0 Study Objectives	4,5
3.0 Selection of Subjects	5
3.1 Inclusion Criteria.....	5
3.2 Exclusion Criteria.....	5
4.0 Subject Registration	5
5.0 Study Design & Methods	5,6
6.0 Statistical Plan	6
7.0 Data Collection & Record Keeping	6
8.0 References	7
Appendices	8

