3.2 EXCLUSION CRITERIA

- Patients undergoing revision surgery, any operations for trauma, infection, tumor
- Patients with general metabolic diseases such as rheumatoid arthritis, diabetes, chronic heart and renal diseases.

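### The stated 2-year duration does not fit the plan's own best-case accrual plus 1-year follow-up (24.5 months for 75 patients, 26.2 for 85), and the accrual figure allows nothing for exclusions or refusals

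*Combined protocol and SAP*

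**What the plan says.** The Synopsis gives "Study Duration 2 years". Section 6.0 says that three named surgeons "perform approximately 6 ACDFs a month" and continues: "This would allow us to collect our proposed sample size in approximately 12-14 months".

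Section 5.0 schedules the dysphagia surveys (EAT-10 and Bazaz, the primary outcome) before surgery, on postoperative day 1, and then at "week 2, week 6, month 3, month 6, and 1 year as a measure of dysphagia".

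The sample size appears in two forms. Section 5.0 says "We intend to prospectively evaluate 85 patients as part of a single blind, randomized controlled study", but also "The 75 envelopes will then be shuffled to create a random assortment". Section 6.0 has "with total sample size 85 (Group I: 25, Group II: 25, Group III: 25", and three groups of 25 make 75.

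Section 3.1 limits inclusion to the patients of three named surgeons and requires signed consent. Section 3.2 excludes revision surgery and operations for trauma, infection or tumor, and also "Patients with general metabolic diseases such as rheumatoid arthritis, diabetes, chronic heart and renal diseases". No eligibility, consent or dropout rate is given anywhere.

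**The concern.** Two features of the timeline stand out. First, the accrual estimate goes straight from operations performed to patients enrolled, although the protocol excludes several groups of ACDF patients and needs consent from the rest. Second, a 12-14 month accrual followed by a 12-month follow-up already fills or exceeds 24 months, so the stated duration has no slack even before any loss.

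What is at stake is the completeness of the 1-year primary-outcome surveys. If someone used the 2 years as a closing date, the patients without a 1-year result would be the last enrolled. Study end also starts another clock: Section 7.0 has identifiable data destroyed a year after the study is complete, and completion is not defined.

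**Working it through.** **Inputs**

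- Monthly volume: about 6 ACDFs (Section 6.0), read as the three surgeons combined.
- N: 85 (Synopsis, Sections 5.0 and 6.0) or 75 (3 x 25 in Section 6.0; envelopes in Section 5.0; the appendix forms also end at 75).
- Follow-up per patient: 12 months (Section 5.0).
- Stated duration: 24 months (Synopsis).
- Fraction of ACDF patients enrolled: not given.

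**Step 1. Reproduce the plan's accrual figure.** Accrual = N / monthly rate.

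- N = 75: 75/6 = 12.5 months.
- N = 85: 85/6 = 14.2 months.

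These match approximately 12-14 months, with 100% of ACDFs enrolled. Reading the rate as 6 per surgeon gives 18 a month and 75/18 = 4.2 to 85/18 = 4.7 months, which does not match. The combined reading is therefore the one the plan used.

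**Step 2. Add follow-up.** Total = accrual + 12 months.

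- N = 75: 12.5 + 12 = 24.5 months.
- N = 85: 14.2 + 12 = 26.2 months.

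The plan's own range gives 12 + 12 = 24 to 14 + 12 = 26 months. Exactly 24 months requires accrual to finish in 12, and 12 x 6 = 72 patients, fewer than either stated N. To finish in 24 months the trial needs 75/12 = 6.25 or 85/12 = 7.08 enrolled patients a month.

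**Step 3. Effect if 24 months were a closing date** (even accrual from month 0, every ACDF enrolled). Patients enrolled after month 12 have no 1-year visit.

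- N = 75: 75 - 72 = 3 patients, 3/75 = 4%.
- N = 85: 85 - 72 = 13 patients, 13/85 = 15%.

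**Step 4. Sensitivity to the enrolled fraction f.** The values of f are assumptions, shown only for the range. Accrual = N / (6f); patients without a 1-year visit by month 24 = N - 72f, rounded.

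| f (assumed) | Accrual, N = 75 / 85 (months) | Total, N = 75 / 85 (months) | No 1-year visit by month 24, N = 75 / 85 |
|---|---|---|---|
| 100% | 12.5 / 14.2 | 24.5 / 26.2 | 3 / 13 |
| 90% | 13.9 / 15.7 | 25.9 / 27.7 | 10 / 20 |
| 80% | 15.6 / 17.7 | 27.6 / 29.7 | 17 / 27 |
| 70% | 17.9 / 20.2 | 29.9 / 32.2 | 25 / 35 |
| 60% | 20.8 / 23.6 | 32.8 / 35.6 | 32 / 42 |

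Accrual within 14 months (14 x 6 = 84 operations) needs f of at least 75/84 = 89% for 75 patients and 85/84 = 101% for 85.

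**The case against.** **The accrual arithmetic is right.** A reader might infer that the 12-14 months is itself a miscalculation. It is not: at 6 a month with everyone enrolled it reproduces. The 24.5 and 26.2 months contradict the Synopsis duration, not the accrual estimate. The complaint about accrual is that it is a best case.

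**The overrun may be small.** With 75 patients it is half a month, against a duration given in whole years and a rate given as approximate. This stands. The larger gap of 2.2 months belongs to N = 85, so much of the size depends on the unresolved conflict between 75 and 85.

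**Other sites may add volume.** The Synopsis lists four centers, and Section 4.0 has each collaborating site recruit. The names are removed from the public copy, so it cannot be confirmed that the three surgeons in Section 6.0 are the same three as in Section 3.1, or how they map to sites. This partly stands: 6 a month may not be the whole trial's capacity. But it is the only volume given, Section 6.0 rests its accrual estimate on it, and Section 3.1 also limits inclusion to three surgeons.

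**Nothing says that follow-up stops at month 24.** True. The Synopsis states a duration, not a closing rule. Section 5.0 describes the 1-year visit as standard care and allows surveys by phone. One year is one of six postoperative time points and is not named as the principal one, so a late or missing 1-year survey would leave the earlier data intact. The chart review in Section 5.0 covers 1/1/2013 to 12/30/2016, which shows that not all data collection is tied to a 24-month window, though it concerns complications and not the surveys. The loss of 1-year outcomes is therefore conditional. The mismatch between duration and schedule is not.

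**Conclusion.** The point holds as an inconsistency in the planned timeline. The plan's own rate, sample size and follow-up give 24.5 months (N = 75) or 26.2 months (N = 85), against a stated 24, and that is with every ACDF enrolled. The accrual figure has no allowance for the Section 3.2 exclusions or for refusal of consent, so the true duration is longer by an amount the documents do not let one calculate.

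Taken literally, a 2-year limit would cost the 1-year outcome in 3 of 75 (4%) to 13 of 85 (15%) patients. This rests on even accrual at 6 a month from the start, no added volume from other surgeons, and a hard stop that the documents do not state.

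A reader might go further and infer that the trial will run to around 28-36 months, or lose the 1-year outcome in a quarter to a half of patients. Those figures need an enrolled fraction of about 60-80%, which appears nowhere in the documents. Nor do the documents show that accrual in 12-14 months is impossible, since volume at the other recruiting sites is not given. On its own, the inconsistency does not affect randomization, the analysis method or the power calculation.

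**What to change.** 1. Settle whether N is 75 or 85, and use one figure throughout.
2. In Section 6.0, restate accrual as N / (monthly ACDF volume across all recruiting surgeons x expected fraction eligible and consenting). State both inputs and where they come from, with volume by site if more than one site contributes.
3. In the Synopsis, restate Study Duration as that accrual plus 12 months. Rounding up the best case, this is at least about 25 months for 75 patients or 27 for 85, and longer once a realistic enrolled fraction is used.
4. State that the study ends at the last patient's 1-year visit. This also fixes when the data-destruction period in Section 7.0 begins.

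The cost is a few lines of text and a longer stated timeline. Apart from settling N, no design element changes.
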